7.1.2. Planned Efficacy Statistical Analyses

Primary Statistical Analyses
Endpoint(s)

 Mean change from baseline in ACQ-5 score at Week 32 (ADaM Dataset : ADACQ5)
Model Specification

 Endpoint will be analysed using a mixed models repeated measures (MMRM) analysis Dependent variable will be ACQ-5 score at each visit including the baseline Terms fitted in the MMRM analysis will include: Fixed Categorical Covariates : Region, Baseline maintenance OCS use, Visit Fixed Continuous Covariates : Exacerbations in the year prior to study (as an ordinal variable), Repeated : Visit See Section 10.10.1 for further details around model covariates.
Model Checking & Diagnostics

 Refer to Appendix 11: Model Checking and Diagnostics for Statistical Analyses.
Model Results Presentation

 Adjusted means and the corresponding 95% confidence intervals will be presented by visit. The estimated adjusted means will be presented using the observed marginal distribution of the sample covariates (OM option in LSMEANS statement). The Kenward and Roger method for approximating the denominator degrees of freedom and correcting for bias in the estimated variance-covariance of the fixed effects will be used (DDMF=KR). An unstructured covariance structure for the R matrix will be used by specifying 'type=UN' on the REPEATED line. Change from the baseline at each Visit X will be calculated by (Estimated Score at Visit X minus Estimated Score at Baseline) and the corresponding 95% confidence intervals. Adjusted means at each visit will also be presented. Plots of LS means change from baseline in ACQ-5 Score and 95% confidence intervals from the model will be generated by visit. Adjusted mean and corresponding standard error of mean will be presented, together with estimated between treatment difference (Mepolizumab – Historical Placebo) and the corresponding 95% confidence intervals at Week 32.
Treatment Phase

 All subjects in the ITT population will be included within this analysis. All data collected up to and including Week 32 from patients, including those who have discontinued study treatment, will be included in the analysis.
Sensitivity and Supportive Statistical Analyses

 Additional comparisons to historical placebo effect will be presented at Week 32 (refer to Section 7.1.3 for more details). A supporting sensitivity analysis of the Per Protocol (PP) population will also be performed. Subgroup analyses of the primary endpoint will be performed for all subgroups listed within Section 10.10.2.

7.1.3. Analysis Comparing Against A Historical Placebo Effect

We will perform two separate analyses of the primary endpoint comparing to a historical 'placebo effect'.

[figure not shown]
Firstly, as specified in the protocol, a meta-analysis of previous exacerbation double-blind studies, MEA112997 and MEA115588, gave an estimate of -0.55 (SE: 0.05), for the improvement in the ACQ-5 score for placebo subjects at Week 32 compared to baseline. The observed improvement in this study for following mepolizumab treatment will be compared to this historical improvement on placebo.

Secondly, a meta-analysis has been performed of subjects within studies MEA115588 and 200862 who reported previous Xolair use, which may represent a more comparable population for this study. Study 200862 has completed since the protocol was finalised and previous Xolair usage was not collected in study MEA112997.

At Week 32 an estimate of -0.29 (SE: 0.248) was reported in the MEA115588 study while at Week 24 study 200862 reported an estimate of -0.03 (SE: 0.164) for the improvement in the ACQ-5 score for placebo subjects who previously used Xolair.

Weighted meta-analysis was performed on these values to get the combined estimate of -0.11 (SE: 0.14) for the historical placebo effect (Figure 1). This shows a reduction in the ACQ-5 score, but not as large as that specified in the protocol. The observed improvement in this study for mepolizumab vs. baseline will be also compared to this historical improvement on placebo.

Figure 1 Meta-analysis of ACQ-5 Placebo Effect in Previous Xolair Users

8. SECONDARY STATISTICAL ANALYSES

8.1 Efficacy Analyses

8.1.1. Overview of Planned Efficacy Analyses

The secondary efficacy analyses will be based on the Intent-To-Treat (ITT) population, unless otherwise specified in [Appendix 13: List of Data Displays](#).

[Table 5](#) provides an overview of the planned efficacy analyses, with further details of data displays being presented in [Appendix 13: List of Data Displays](#).

Table 5 Overview of Planned Efficacy Analyses

Endpoint	Absolute ^[1]						Change from Baseline ^{[1] [2]}						
	Stats Analysis			Summary		Individual	Stats Analysis			Summary		Individual	
	T	F	L	T	F	F	L	T	F	L	T	F	F
Secondary Endpoints													
St George's Respiratory Questionnaire (SGRQ)													
On-treatment & Off-treatment	Y			Y				Y	Y		Y	Y	
Blood Eosinophil Count													
On-treatment & Off-treatment	Y			Y				Y	Y		Y		
On-treatment ^[3]	Y							Y					
Other Endpoints													
>= 0.5-point reduction from baseline in ACQ-5 score at Week 32													
On-treatment & Off-treatment										Y	Y		
>= 4-point or greater reduction from baseline in SGRQ Total score at Week 32													
On-treatment & Off-treatment										Y	Y		
Pre-Bronchodilator FEV1													
On-treatment & Off-treatment	Y			Y				Y	Y		Y		
Post-Bronchodilator FEV1													
On-treatment & Off-treatment	Y			Y				Y	Y		Y		
Subject/Clinician Rated Response to Therapy													
On-treatment ^[3]				Y									
Treatment Satisfaction Questionnaire for Medication (TSQM-9)													
On-treatment ^[3]				Y						Y			
Biomarkers													
On-treatment				Y						Y			

Endpoint	Incidence of Events						
	Stats Analysis			Summary		Individual	
	T	F	L	T	F	F	L
Secondary Endpoints							
Clinically Significant Exacerbations							
On-treatment & Off-treatment	Y ^[4]			Y	Y		Y
On-treatment ^[3]	Y ^[4]						
Exacerbations requiring ED visit/hospitalization							
On-treatment & Off-treatment	Y ^[4]			Y			Y
On-treatment ^[3]	Y ^[4]						
Exacerbations requiring hospitalization							
On-treatment & Off-treatment	Y ^[4]			Y			Y

NOTES :

- T = Table, F = Figure, L = Listing, Y = Yes display generated.
- Stats Analysis = Represents TFL related to any formal statistical analyses (i.e. modelling) conducted.
- Summary = Represents TFL related to any summaries (i.e. descriptive statistics) of the observed raw data.
- Individual = Represents FL related to any displays of individual subject observed raw data.

1. Absolute and change from baseline summaries combined into a single display.
2. Ratio to Baseline to be shown for Blood Eosinophil Count and Biomarker data.
3. To analyse data collected whilst On-Treatment, not considering any data collected following treatment discontinuation (see Section 10.4).
4. Table to include annualised exacerbation rate and 95% confidence intervals from negative binomial model.

8.1.2. Secondary Efficacy Statistical Analyses

Secondary Statistical Analyses
Secondary Endpoint(s)

 Mean change from baseline in SGRQ at Week 32
Model Specification

 See Primary Efficacy Statistical Analysis, Section 7.1.2
Model Checking & Diagnostics

 Refer to Appendix 11: Model Checking and Diagnostics for Statistical Analyses.
Model Results Presentation

 Adjusted means and the corresponding 95% confidence intervals will be presented by visit. The estimated adjusted means will be presented using the observed marginal distribution of the sample covariates (OM option in LSMEANS statement). The Kenward and Roger method for approximating the denominator degrees of freedom and correcting for bias in the estimated variance-covariance of the fixed effects will be used (DDMF=KR). An unstructured covariance structure for the R matrix will be used by specifying 'type=UN' on the REPEATED line. Change from the baseline at each Visit X will be calculated by (Estimated Score at Visit X minus Estimated Score at Baseline) and the corresponding 95% confidence intervals. Adjusted means at each visit will also be presented. Plots of LS means change from baseline in SGRQ Score and 95% confidence intervals from the model will be generated by visit.
On-treatment Phase

 See Primary Efficacy Statistical Analysis, Section 7.1.2

Secondary Statistical Analyses
Secondary Endpoint(s)

 Frequency of clinically significant asthma exacerbations over 32 week treatment Frequency of exacerbations requiring ED visit/hospitalization during the 32 week treatment period Frequency of exacerbations requiring hospitalization during the 32 week treatment period
Model Specification

 The frequency of clinically significant exacerbations will be analysed using Negative Binomial regression via generalised estimating equations with a covariate of time period (pre-, post-mepolizumab). Exacerbations separated by less than 7 days will be treated as a continuation of the same exacerbation. The pre-mepolizumab exacerbation values (in the 12 months prior) will be obtained at screening, while the post-mepolizumab exacerbation values will be observed during the study. The variance of the mean estimate will be corrected for within-subject correlation. The logarithm of time on treatment will be used as an offset variable.
Model Checking & Diagnostics

 Refer to Appendix 11: Model Checking and Diagnostics for Statistical Analyses.

Secondary Statistical Analyses
Model Results Presentation

 Adjusted exacerbation rate and the corresponding 95% confidence interval will be presented.
On-treatment Phase

 All subjects in the ITT population will be included within this analysis. All data collected up to and including Week 32 from patients, including those who have discontinued study treatment, will be included in the analysis. An On-Treatment “de jure” analysis will also be performed which does not consider any data collected following treatment discontinuation (see On-Treatment definition within Section 10.4).
Sensitivity and Supportive Statistical Analyses

 The On-Treatment “de jure” analysis will be also performed with a subset of patients who were on omalizumab for more than 12 months.

Secondary Statistical Analyses
Secondary Endpoint(s)

 Ratio to baseline in blood eosinophil count at week 32
Model Specification

 See Primary Efficacy Statistical Analysis, Section 7.1.2 A log-transformation will be applied to blood eosinophil count data prior to analysis. If a blood eosinophil count of zero is reported, it will be imputed with half of the lowest possible blood eosinophil count, where applicable, prior to log transforming the data (Note: this imputation has typically been $0.5 * 0.01 \text{ GI/L} = 0.005 \text{ GI/L}$ for previous mepolizumab studies).
Model Checking & Diagnostics

 Refer to Appendix 11: Model Checking and Diagnostics for Statistical Analyses..
Model Results Presentation

 Adjusted means and the corresponding 95% confidence intervals will be presented by visit. Plots of LS means ratio to baseline in blood eosinophil count and 95% confidence intervals from the model will be generated by visit.
On-treatment Phase

 All subjects in the ITT population will be included within this analysis. All data collected up to and including Week 32 from patients, including those who have discontinued study treatment, will be included in the analysis. An On-Treatment “de jure” analysis will also be performed which does not consider any data collected following treatment discontinuation (see On-Treatment definition within Section 10.4).

Other Statistical Analyses
Other Endpoint

 Percentage of subjects achieving a 0.5-point or greater reduction from baseline in ACQ-5 score at Week 32
Results Presentation

 The number and percentage of subjects achieving a 0.5-point or greater reduction in ACQ-5 Score compared to baseline will be presented for each visit. The number of subjects with a missing ACQ-5 Score at each visit will be presented in a separate category.

On-treatment Phase
• See Primary Efficacy Statistical Analysis, Section 7.1.2

Other Statistical Analyses
Other Endpoint
• Percentage of subjects achieving a 4-point or greater reduction from baseline in SGRQ score at Week 32
Results Presentation

 The number and percentage of subjects achieving a 4-point or greater reduction in SGRQ Total score compared to baseline will be presented for each visit. The number of subjects with a missing SGRQ Total Score at each visit will be presented in a separate category.
On-treatment Phase
• See Primary Efficacy Statistical Analysis, Section 7.1.2

Other Statistical Analyses
Other Endpoint
• Mean change from baseline in pre- and post- bronchodilator FEV1 at Week 32
Model Specification
• See Primary Efficacy Statistical Analysis, Section 7.1.2
Model Checking & Diagnostics
• Refer to Appendix 11: Model Checking and Diagnostics for Statistical Analyses .
Model Results Presentation

 Adjusted means and the corresponding 95% confidence intervals will be presented by visit The estimated adjusted means will be presented using the observed marginal distributions of the sample covariates (OM option in LSMEANS statement). The Kenward and Roger method for approximating the denominator degrees of freedom and correcting for bias in the estimated variance-covariance of the fixed effects will be used (DDMF=KR). An unstructured covariance structure for the R matrix will be used by specifying 'type=UN' on the REPEATED line. Change from the baseline at each Visit X will be calculated by (Estimated Score at Visit X minus Estimated Score at Baseline) and the corresponding 95% confidence intervals. Adjusted means at each visit will also be presented. Plots of Least Squares (LS) mean change from baseline pre- and post bronchodilator FEV1 and 95% confidence intervals from the model will be generated at each visit.
On-treatment Phase
• See Primary Efficacy Statistical Analysis, Section 7.1.2

Other Statistical Analyses
Other Endpoint
• Subject rated response to therapy at Week 32
• Clinician rated response to therapy at Week 32
Results Presentation

 • The number and percentage of subjects in each response category will be presented for each visit. • The number of subjects with a missing responses at each visit will be presented in a separate category.
--

On-treatment Phase

 • An On-Treatment “de jure” analysis will also be performed which does not consider any data collected following treatment discontinuation (see On-Treatment definition within Section 10.4).

Other Statistical Analyses

Other Endpoint

 • Mean change from baseline in Treatment Satisfaction Questionnaire for Medication (TSQM-9)

Model Specification

 • The Mean Change at Week 32 will be tested to see if it is significantly different from zero using Wilcoxon signed-rank test

Model Checking & Diagnostics

 • Check for the extreme outliers by plotting the differences between TSQM-9 at Week 32 and Baseline

Model Results Presentation


 • Summary Statistics will be represented by study visit • The mean change at Week 32 will presented with the corresponding 95% CI and p-value in the table • The mean change at Week 32 will presented with the corresponding 95% CI in the figure
--

On-treatment Phase

 • An On-Treatment “de jure” analysis will also be performed which does not consider any data collected following treatment discontinuation (see On-Treatment definition within Section 10.4)
--

Other Statistical Analyses

Other Endpoint

 • Change from baseline in inflammatory biomarkers expression at week 32. The following biomarker parameters will be reported: CCL13, CCL17, ECP, EDN, Eotaxin1, Total IL-5, IL-13, MDC, Periostin, TSLP

Model Results Presentation

 • A log-transformation will be applied to each biomarker parameter prior to analysis. • Summary Statistics will be represented by study visit, including ratio to baseline • See Section 10.6.4 for further information regarding biomarker results below the lower limit of quantification

On-treatment Phase

 • An On-Treatment “de jure” analysis will also be performed which does not consider any data collected following treatment discontinuation (see On-Treatment definition within Section 10.4).

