6.	Controller Medication: Current treatment with an additional controller medication, besides ICS, for at least 3 months or a documented failure in the past 12 months of an additional controller medication for at least 3 successive months. [e.g., long-acting beta-2-agonist (LABA), leukotriene receptor antagonist (LTRA), long-acting anticholinergic (tiotropium bromide), or theophylline.]
7.	Asthma symptoms not optimally controlled: An ACQ-5 score of $\geq 1.5$ recorded at Visit 1.
8.	Omalizumab Treatment: Receiving omalizumab, based on weight and IgE levels, for at least the 4 months prior to Visit 1.
9.	Exacerbation history: Previously confirmed history of two or more exacerbations requiring treatment with systemic corticosteroids (intramuscular, intravenous, or oral) in the 12 months prior to Visit 1 despite the use of high-dose ICS. For subjects receiving omalizumab for $\geq 8$ months, at least one exacerbation must have occurred while on omalizumab treatment. For subjects receiving maintenance oral corticosteroids, the corticosteroid treatment for the exacerbations must have been a two-fold dose increase or greater.

SEX
10. Male or eligible Female
Females:
a. Non-reproductive potential defined as:

 
• Pre-menopausal females with one of the following:           
 
• Documented tubal ligation
 
• Documented hysteroscopic tubal occlusion procedure with follow-up confirmation of bilateral tubal occlusion
 
• Hysterectomy
 
• Documented Bilateral Oophorectomy
 
 
 
• Postmenopausal defined as 12 months of spontaneous amenorrhea [in questionable cases a blood sample with simultaneous follicle stimulating hormone (FSH) and estradiol levels consistent with menopause (refer to laboratory reference ranges for confirmatory levels)]. Females on hormone
 

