## **6.8. Concomitant Medications and Non-Drug Therapies**

### **6.8.1. Permitted Medications and Non-Drug Therapies**

Throughout the study, subjects are to be maintained on their baseline standard of care asthma treatment. The only exception to this is the discontinuation of omalizumab from Visit 2 onwards.

Additional asthma medications such as theophyllines or anti-leukotrienes will be permitted provided that they have been taken regularly in the 3 months prior to first dose of mepolizumab treatment (Visit 2, Week 0).

All concomitant medications taken during the study will be recorded in the eCRF. In addition, all medications taken by the patient for the treatment of asthma including asthma exacerbations in the 12 months prior to Visit 1 must also be recorded in the eCRF. The minimum requirement is that the drug name and the dates of administration are recorded. However, for ICS/LABA, omalizumab and OCS, the dose and regimen (including any change in dose or regimen) must also be recorded. Continuous Positive Airway Pressure (CPAP) for the treatment of obstructive sleep apnea is permitted, if initiated prior to the Screening Visit 1.

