### **7.3.2.4. Clinically Significant Asthma Exacerbation**

***Clinically significant exacerbations of asthma are defined by:***

Worsening of asthma which requires use of systemic corticosteroidsand/or hospitalisation and/or Emergency Department (ED) visits.

*For all subjects, i.v. or oral steroid (e.g., prednisone) for at least 3 days or a single IM CS dose is required. For subjects on maintenance systemic corticosteroids, at least double the existing maintenance dose for at least 3 days is required.*

Exacerbation data will be included in the analysis from Visit 2 until Exit Visit (Week 32) approximately 4 weeks after the last dose of study treatment. For those subjects that stop study treatment early or withdraw early from the study altogether, the time period for collection of exacerbation data will be from Visit 2 until no greater than approximately 4 weeks post-last-dose of mepolizumab. For consistency, exacerbations separated by less than 7 days will be treated as a continuation of the same exacerbation.

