2. SUMMARY OF KEY PROTOCOL INFORMATION

2.1. Changes to the Protocol Defined Statistical Analysis Plan

Statistical analysis changes to the originally planned statistical analysis specified in the protocol amendment 1 (Dated: 23-MAR-2016) (GSK Document No.: [2015N243304_01](#)) are outlined in [Table 1](#).

Table 1 Changes to Protocol Defined Statistical Analysis Plan

Protocol	Reporting & Analysis Plan	Rational for Changes
Statistical Analysis Plan	Statistical Analysis Plan	

 Analysis of change from baseline in ACQ, SQRQ scores will be performed using a mixed models repeated measures (MMRM) analysis, allowing for covariates of baseline ACQ score, region, baseline maintenance OCS therapy, exacerbations in the year prior to the study (as an ordinal variable), visit and an interaction term for visit by baseline ACQ score. Clinically significant exacerbations will be analyzed using a generalized linear model with covariates for region, baseline maintenance OCS therapy and number of exacerbations in the year prior to the study (as an ordinal variable). 	
 Baseline values will be included as a data point in the analysis, and there will be no covariate adjustment made in the model. The change from the baseline at Visit X will be calculated by: Estimated Score at Visit X minus Estimated Score at Baseline. Clinically significant exacerbations will be examined using a generalized estimating equation (GEE) with no adjustments for covariates. 	
 This is a single treatment arm study and comparisons are being made directly to the baseline values. Generalised estimating equations (GEEs) will compare the on-treatment exacerbation rate to the rate within the 12 months prior to study.

[figure not shown]

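### The pre/post-mepolizumab exacerbation comparison does not require the 12-month history to meet the on-study event definition, so the two rates may not be comparable; the direction of any bias is unknown

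*SAP*

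**What the plan says.** - **The comparison.** SAP 2.1 replaces the protocol's exacerbation model with generalised estimating equations that will "compare the on-treatment exacerbation rate to the rate within the 12 months prior to study". In SAP 8.1.2 the only covariate is period, before or after mepolizumab.
- **Source of the two counts.** SAP 8.1.2: "pre-mepolizumab exacerbation values (in the 12 months prior) will be obtained at screening", "while the post-mepolizumab exacerbation values will be observed during the study".
- **Historical events.** Protocol 5.1, inclusion criterion 9, asks for a "history of two or more exacerbations requiring treatment with systemic corticosteroids (intramuscular, intravenous, or oral) in the 12 months prior to Visit 1". Maintenance oral corticosteroid users need at least a two-fold dose increase. No minimum number of days is given, and ED visits or admissions without steroids are not mentioned. At screening, protocol 7.2.2 collects rescue steroid courses and exacerbation history for the past year, again without a duration threshold.
- **On-study events.** Protocol 7.3.2.4 and SAP 10.6.3 count a worsening that needs systemic steroids and/or hospitalisation and/or an ED visit. For the steroid route, "i.v. or oral steroid (e.g., prednisone) for at least 3 days or a single IM CS dose is required"; maintenance users need at least a doubled dose for at least 3 days. Protocol 7.3.2.4 describes its analysis data as running from Visit 2.
- **Merging.** Protocol 7.3.2.4: "exacerbations separated by less than 7 days will be treated as a continuation of the same exacerbation". SAP 8.1.2 and 10.6.3 repeat this with no restriction to either period.
- **Data available.** Protocol 6.8.1 requires the eCRF to hold all "medications taken by the patient for the treatment of asthma including asthma exacerbations in the 12 months prior to Visit 1", with drug name and dates as a minimum, and dose and regimen for oral corticosteroids.

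**The concern.** There is no control arm, so the before/after ratio is the only comparative exacerbation result the trial will produce. Such a ratio is interpretable only if the same kind of event is counted on both sides of the switch. As written, the plan allows different kinds. A 2-day oral course with no ED visit or admission fits the historical criterion but not the on-study definition. An ED visit without qualifying steroids fits the on-study definition but not the historical criterion. The collapsing step in SAP 10.6.3 works from start and end dates of episodes, and nothing says how it is carried out on a history taken at screening. Any resulting difference enters the rate ratio directly and cannot be told apart from a treatment effect.

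**Working it through.** The documents give no rate, effect size or power for the exacerbation comparison, so there is no figure to reproduce. The check sets the texts side by side and then illustrates the size.

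**Step 1: the two definitions**

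| Feature | History (inclusion 9) | On study (7.3.2.4, SAP 10.6.3) |
|---|---|---|
| Oral or i.v. steroid | any duration | at least 3 days |
| Single i.m. dose | counts | counts |
| Maintenance steroid users | at least two-fold increase, any duration | at least doubled, at least 3 days |
| ED or hospital event without steroids | not mentioned | counts |
| 7-day merging | stated in the SAP without period limit; method for the history not given | stated, with a dated procedure |

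Inclusion 9 does not refer to 7.3.2.4, whereas continuation criterion 2 in protocol 5.3 does. The study definition therefore cannot simply be read into the history.

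**Step 2: ratio due to definitions alone, with no true change**

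Let s be the share of historical-type events that fail the 3-day rule, m the share lost if merging happened only on study, and b the ED/hospital-only events that count only on study, as a fraction of historical-type events. Then

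RR = (1 − s)(1 − m) + b.

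None of s, m or b is in the documents; all values below are assumptions. With merging in both periods (m = 0):

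- s = 20%, b = 0: 0.80
- s = 10%, b = 0: 0.90
- s = 10%, b = 10%: 0.90 + 0.10 = 1.00
- s = 5%, b = 10%: 0.95 + 0.10 = 1.05
- s = 0, b = 10%: 1.10

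If merging were in practice applied only on study, m = 5% with s = 10% and b = 0 would give 0.90 × 0.95 = 0.855. One definition and one merging rule in both periods give 1.00.

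**Step 3: what a net artefact could do to the test**

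Take 120 subjects, one year before and 32/52 year after, pre-rate r of 2.5 to 3.5 per year, dispersion d of 0 to 0.5, and independent periods. The rates, dispersion and independence are assumptions.

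Var(log RR) = (1/r + d)/120 + (1/(r × RR × 32/52) + d)/120.

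For r = 2.5, d = 0.5, RR = 0.90: (0.4 + 0.5)/120 + (0.722 + 0.5)/120 = 0.0177, so SE = 0.133. Then |ln 0.90|/SE = 0.105/0.133 = 0.79, and the chance of a nominally significant fall at the two-sided 5% level is about 12%. Across the assumed grid it is about 12% to 25% at RR 0.90 and about 38% to 75% at RR 0.80. A net artefact above 1.00 would work the other way and mask part of a real fall.

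**The case against.** The best defence is that the plan intends one definition throughout. SAP 8.1.2 calls the outcome clinically significant exacerbations without distinguishing periods, SAP 10.6.3 defines an exacerbation without limiting it to on-study events, and SAP 10.4.1 has a pre-treatment phase for exacerbation data. Inclusion 9 is an entry threshold, not a declared definition of the analysed count. Protocol 7.2.2 collects exacerbation history separately from steroid courses, so historical ED or hospital events may be captured. The protocol's objective is the frequency on mepolizumab, and the on-study rate rests on prospectively observed events.

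Much of this stands, and it rules out several stronger readings that a reader might infer:

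- *Merging applies only after the switch.* The SAP states the rule with no period limit; only its application to the history is unspecified.
- *Only courses of at least 3 days count on study.* A single intramuscular dose counts, and so does a hospitalisation or ED visit.
- *Part of any fall comes from the definition.* The ED/hospital route pushes the opposite way to the duration rule, so the sign is not fixed.
- *The plan declares two different definitions.* It leaves the historical one unstated.

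What the defence does not supply is any sentence requiring the screening history to meet the on-study rule, or a step that checks it. The one criterion that is stated for historical events differs in two respects.

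**Conclusion.** The point holds as a gap in specification: the historical count is not required to meet the on-study definition, and following the plan as written can compare differently defined events. The direction and size of any bias are unknown. The range of about 0.80 to 1.10 is illustrative and rests wholly on assumed shares (s up to 20%, b up to 10%, merging in both periods).

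The issue affects a secondary endpoint and leaves the ACQ-5 analysis untouched. It should be settled before database freeze, because the before/after ratio is the trial's only exacerbation contrast. It is separate from regression to the mean caused by requiring at least two prior exacerbations. That effect may well be larger: a gamma-Poisson illustration with assumed population means of 1 to 3 per year and dispersion 0.5 to 1 gives ratios of about 0.58 to 0.90 with no treatment effect. A common definition does not remove it.

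**What to change.** 1. In SAP 8.1.2 and 10.6.3, state that one event definition and one 7-day merging rule apply to both periods, and say how they are applied to the 12-month history.
2. Add a supportive pre/post analysis limited to steroid-treated events that meet the on-study duration, single intramuscular dose or doubling rule in both periods. Derive the historical events from the dated medication records required by protocol 6.8.1. This should be supportive rather than the main contrast, because it drops the ED/hospital route of the pre-specified endpoint.
3. Keep reporting the on-study rate under the full 7.3.2.4 definition, and show ED/hospital-only events separately.
4. Do not let the partial-date imputation in SAP 10.7.2.1 decide the 3-day test. It sets missing days to the start or end of the month, so a course known only to have started and ended in March would become 31 days and pass automatically. Run the supportive analysis with such courses counted, then with them excluded.

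The cost is SAP wording and programming from data the protocol already requires. The remaining weakness is that some historical courses cannot be classified, which the two runs in item 4 make visible.
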